7.2.5 Efficacy in Surgical Prophylaxis

Efficacy will be assessed at the end of surgery by the surgeon (see **Section 7.2.5.1**) and at end of the postoperative period by the hematologist (see **Section 7.2.5.2**). In both cases, predefined assessment criteria will be used.

In addition, there will be an overall assessment of efficacy (see **Section 7.2.5.3**).

7.2.5.1 At the End of Surgery (by Surgeon)

At the end of surgery, the hemostatic efficacy of *Wilate* will be assessed by the surgeon using the criteria listed in **Table 3**.

Table 3 Efficacy Assessment at the End of Surgery

Excellent	Intraoperative blood loss was lower than or equal to the average expected blood loss for the type of procedure performed in a patient with normal hemostasis and of the same sex, age, and stature.
Good	Intraoperative blood loss was higher than the average expected blood loss but lower or equal to the maximal expected blood loss for the type of procedure in a patient with normal hemostasis.
Moderate	Intraoperative blood loss was higher than the maximum expected blood loss for the type of procedure performed in a patient with normal hemostasis, but hemostasis was controlled.
None	Hemostasis was uncontrolled, necessitating a change in the clotting factor replacement regimen.

7.2.5.2 At the End of the Postoperative Period (by Hematologist)

At the end of the postoperative period, the hemostatic efficacy of *Wilate* will be assessed by the hematologist using the criteria listed in **Table 4**.

Table 4 Efficacy Assessment at the End of the Postoperative Period

Excellent	No postoperative bleeding or oozing that was not due to complications of surgery. All postoperative bleeding (due to complications of surgery) was controlled with Wilate as anticipated for the type of procedure.
Good	No postoperative bleeding or oozing that was not due to complications of surgery. Control of postoperative bleeding due to complications of surgery required increased dosing with Wilate or additional injections not originally anticipated for the type of procedure.
Moderate	Some postoperative bleeding and oozing that was not due to complications of surgery. Control of postoperative bleeding required increased dosing with Wilate or additional injections not originally anticipated for the type of procedure.
None	Extensive uncontrolled postoperative bleeding and oozing. Control of postoperative bleeding required use of an alternate FVIII concentrate.

7.2.5.3 Overall Efficacy Assessment at the End of the Postoperative Period (by Investigator)

Overall efficacy using the ‘excellent,’ ‘good,’ moderate,’ and ‘none’ scale taking both the intra- and postoperative assessments into account will be assessed by the Investigator.

Table 5 Algorithm for the Overall Efficacy Assessment for Surgical Prophylaxis

Intraoperative assessment	Postoperative assessment			
	Excellent	Good	Moderate	None
Excellent	Excellent	Good	Good	Moderate
Good	Good	Good	Moderate	Moderate
Moderate	Good	Moderate	Moderate	None
None	Moderate	Moderate	None	None

7.2.6 Pharmacokinetic Evaluation

The following PK parameters for FVIII:C will be determined:

- AUC_{norm} and AUC
- In vivo half-life ($T_{1/2}$)
- Maximum plasma concentration (C_{max})
- Time to reach maximum plasma concentration (T_{max})
- Mean residence time (MRT)
- Volume of distribution (Vd)
- Clearance (CL)
- Incremental in vivo recovery (IVR)

For details on the laboratory analyses, see **Section 7.3.5**.

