5.4 Dose and Dosing Schedule

5.4.1 PK Assessment Phases

In the 2 PK Assessment Phases performed in a subset of 20 patients before the start and after the end of the Prophylactic Treatment Phase, *Wilate* will be administered to all 20 patients as a single dose of 50 ± 5 IU/kg BW. Full vials should be used. The dose can be rounded to the next higher or lower full vial.

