5.5 Preparation and Method of Administration

For more information on the method of administration of *Wilate*, please see the European Summary of Product Characteristics.

Throughout the study, several batches of *Wilate* will be used, and these will be recorded in the clinical study report.

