6.1.2 PK Visit

Patients will receive *Wilate* at a dose of 50 ± 5 IU/kg (labelled dose) after a washout period of at least 72 hours from their last FVIII injection. Patients must not be experiencing any bleeding.

The following assessments will be performed:

- **Body weight** before injection
- Blood samples will be taken for the following purposes and at the following time points:
 - **FVIII:C plasma concentration (OS and CHR) for PK assessment** within 1 h before injection and 15 ± 5 min, 1 h (± 5 min), 3 h (± 15 min), 6 h (± 30 min), 9 ± 1 h, 24 ± 2 h, 30 ± 2 h, and 48 ± 2 h after the end of injection
 - **Safety laboratory** before and 48 ± 2 h after injection
 - **FVIII inhibitor** before injection
 - Plasma **VWF:Ag** and **VWF:Ac** within 1 h before injection and 15 ± 5 min after the end of injection
 - **Parvovirus B19 antibodies** before injection
 - **Retention sample** for possible additional virus marker testing before injection
- **Vital signs** before injection as well as 1 h (± 5 min) and 48 ± 2 h after injection
- **AE monitoring**
- **Concomitant medications**

At the end of this visit, patients will **receive a patient diary**. The Investigator will explain to the patient how to fill in the diary and emphasize the importance of carefully documenting all treatment details, AEs, and concomitant medications. Also, patients will be **provided with IMP** for home treatment. They will be re-supplied whenever necessary during the study.

The first prophylactic injection of *Wilate* after the PK Visit marks the beginning of the Prophylactic Treatment Phase.

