6.1.7 PK Study Completion Visit

The PK Study Completion Visit will take place 6 months (+2 weeks) after the start of the Prophylactic Treatment Phase.

Patients will receive *Wilate* at a dose of 50 ± 5 IU/kg (labelled dose) after a washout period of at least 48 hours from their last FVIII injection. Patients must not be experiencing any bleeding.

The following assessments will be performed:

- **Review of patient diary**
- **Body weight** before injection
- Blood samples will be taken for the following purposes and at the following time points:
 - **FVIII:C plasma concentration (OS and CHR) for PK assessment** within 1 h before injection and 15 ± 5 min, 1 h (± 5 min), 3 h (± 15 min), 6 h (± 30 min), 9 ± 1 h, 24 ± 2 h, 30 ± 2 h, and 48 ± 2 h after the end of injection
 - **Safety laboratory** before and 48 ± 2 h after injection
 - **FVIII inhibitor** before injection
 - Plasma **VWF:Ag** and **VWF:Ac** within 1 h before injection and 15 ± 5 min after the end of injection
- **Vital signs** before injection as well as 1 h (± 5 min) and 48 ± 2 h after injection
- **AE monitoring**
- **Concomitant medications**
- **Physical examination**
- **Parvovirus B19 antibodies** before injection, if first sample was negative

All used and unused IMP vials will be returned by the patient.

Patients prematurely withdrawing from the study for any reason will also be invited to attend the PK Study Completion Visit.

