5.8 Pharmacokinetics / Pharmacodynamics

For Pharmacokinetics and IVR assessments FVIII:C will be measured by both, the chromogenic (CHR) and one-stage assay (OS) and analyzed based on actual IMP potency.

The PK profiles of *Wilate* and the PK parameters derived from them will be summarized by descriptive statistics as well as the presentation of concentration vs. time plots based on the PK set. In the analysis of the PK profiles geometric means and standard deviations will be presented in addition to the arithmetic means and standard deviations.

The following PK parameter will be derived and presented using a non-compartment model:

- Area under the curve (AUC) and AUC normalized for the administered dose (AUC_{norm})
- FVIII in vivo half-life ($T_{1/2}$)
- Maximum plasma concentration (C_{max})
- Time to reach maximum plasma concentration (T_{max})
- Mean residence time (MRT)
- Volume of distribution (Vd)
- Clearance (CL)
- Incremental in vivo recovery (IVR)

Analysis of variance (ANOVA) will be used in an exploratory sense to assess a possible association between AB0 blood type, VWF:Ag, and the FVIII:C half-life of *Wilate*.

IVR will be analyzed for the FAS and additionally for the PP population if these populations differ by >5%. The results of the IVR assessments over time will be analyzed in summary tables for each time point and their differences to baseline along with 95% CIs for the mean differences.

To compare the pharmacokinetic characteristics of the 6-months PK-profile with those of the baseline PK-profile a matched-pairs sign rank test of the null hypothesis of no time difference will be performed at for all PK parameters.

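### The 6-month versus baseline PK test includes raw AUC and raw Cmax, which move with the delivered dose, and that dose is not fixed between the two visits

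*Protocol*

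**What the plan says.** Protocol 7.2.6 and SAP 5.8 list the FVIII:C parameters: AUC and AUCnorm, half-life, peak ("Maximum plasma concentration (C_{max" opens the protocol entry), Tmax, MRT, Vd, CL and IVR. The only comparison of the two PK profiles over time is in SAP 5.8: "a matched-pairs sign rank test of the null hypothesis of no time difference will be performed at for all PK parameters". That sentence gives no level, so the general 0.050 rule in SAP section 5 applies.

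On dose:
- The baseline injection is given "at a dose of 50 ± 5 IU/kg (labelled dose) after a washout period of at least 72 hours" (Protocol 6.1.2).
- The closing injection is given "at a dose of 50 ± 5 IU/kg (labelled dose) after a washout period of at least 48 hours" (Protocol 6.1.7).
- Full vials are used: "The dose can be rounded to the next higher or lower full vial" (Protocol 5.4.1). Vials hold nominally 500 or 1000 IU (Protocol 5.1).
- Over the study "several batches of *Wilate* will be used" (Protocol 5.5).

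No section requires a patient to receive the same dose or the same batch at both PK visits. The central laboratory assays the vials (Protocol 7.3.5.1), so the actual dose is known for the analysis.

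**The concern.** The SAP's null hypothesis is that nothing changed over time. For raw AUC and raw Cmax it can be false merely because the delivered dose changed. Batches in use at month 6 with a different actual potency from those at baseline would move most patients the same way. Two parameters under two assays give four p-values open to this. PK at baseline and after 6 months is a stated secondary objective, so a reader of the report may take such a p-value as evidence that FVIII kinetics altered under prophylaxis. Dose differences that vary at random between patients do a lesser harm: they add noise and hide a real change.

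**Working it through.** The plan states no power or effect size for the PK comparison, so there is no figure to reproduce.

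**1. Where dose enters.** SAP 8.1 builds AUC from concentrations and defines Cmax as the highest measured concentration. The actual dose D enters CL and IVR, and AUCnorm is normalised for dose. Rearranging the SAP's own formulas:
- CL = D / AUC, so AUC = D / CL. With CL unchanged, AUC moves in proportion to D.
- IVR = (Cmax − C0) × BW / D, so Cmax = C0 + IVR × D / BW. With IVR unchanged, Cmax moves with the IU/kg given.

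**2. How far the labelled dose can differ.** The limits are 45 and 55 IU/kg.
- 55/45 − 1 = +22.2%
- 45/55 − 1 = −18.2%

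These are extremes. Multiples of 500 IU that fall within 45–55 IU/kg at a stable weight:

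| Weight | Doses that fit | Largest difference |
|---|---|---|
| 50, 60, 70, 80, 90 kg | one | none |
| 55 kg | 2500, 3000 IU | 20% |
| 65 kg | 3000, 3500 IU | 17% |
| 75 kg | 3500, 4000 IU | 14% |
| 100 kg | 4500, 5000, 5500 IU | 22% |

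Of the 42 whole-kilogram weights from 40 to 81 kg, 9 (55, 64–66 and 73–77 kg) allow two doses, one (45 kg) allows none, and the other 32 allow exactly one. A second dose is commonly available only at higher weights. Potency differences between batches come on top of this; the documents give no range for them.

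**3. Effect on the test.** Simulation with 20 pairs, two-sided Wilcoxon signed-rank test at 0.05, log-normal within-patient error and exposure proportional to dose. The CVs and the common shifts are assumptions.

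*Dose drawn independently from 45–55 IU/kg at each visit, no PK change:* raw values reject in about 5% of trials (4.4–5.2% across runs). There is no false signal.

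*Same random dosing, true 10% rise, CV 10%:* power on raw values falls from about 79% to about 67% (65–67% across runs). Divided by the actual dose, it stays at about 77%.

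*Delivered dose 10% different in every patient, no PK change:*

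| Within-patient CV | Raw values reject | After division by actual dose |
|---|---|---|
| 8% | about 93–96% | about 5% |
| 10% | about 79–86% | about 5% |
| 15% | about 46–54% | about 5% |
| 20% | about 28–34% | about 5% |

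The lower ends belong to a rise in dose and the upper ends to a fall. Runs differ by a few percentage points; the lowest at CV 15% was 42%. With a common 5% shift the rates are about 27–29% at CV 10% and 10–12% at CV 20%.

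**The case against.** The strongest reply is that the safeguard is already in the same analysis. AUCnorm, CL and IVR are tested by the same method and use the actual dose; IVR is in effect the peak divided by IU/kg, with the pre-dose level removed. If only the dose changed, raw AUC and Cmax would shift while these three stayed put, and a careful reader would see why. That stands, and it limits the harm. But the SAP does not say which result governs when AUC and AUCnorm disagree, so the explanation would come after the results are known.

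A reader might go further and infer that any dose or batch difference will be reported as a PK change, or that differences near 20% are to be expected. The documents support neither. Unsystematic differences leave the error rate at about 5%. Nothing in the plan indicates that batches at month 6 will differ in potency or that weights will drift together. At many body weights only one whole-vial dose fits the window.

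The stakes are also modest. The PK analysis is largely descriptive, the listed PK endpoints are the baseline parameters and IVR over time, and no decision rests on these p-values. The protocol version at hand contains no over-time PK test. The SAP cites a later protocol dated 2017-09-07, which is not among the documents. This bears on severity; it does not change what SAP 5.8 says.

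**Conclusion.** The point holds in a limited form. Read as written, SAP 5.8 tests two parameters for a time effect although they carry the delivered dose and that dose is free to differ between visits. Rejection for raw AUC or raw Cmax cannot be attributed to pharmacokinetics without looking at the dose-adjusted parameters. With random dose differences the cost is power only, about 12 percentage points in the case shown (79% to 67%). With a systematic shift the false-positive rate can be large, but its size depends wholly on shifts and CVs that the documents do not give. Low severity: the comparison is exploratory, the artefact could be recognised, and the primary endpoint is not involved.

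**What to change.** In SAP 5.8, limit the month-6 versus baseline test to AUCnorm, CL, IVR, T1/2, MRT, Vd and Tmax, and state that raw AUC and raw Cmax are summarised by visit without a time-comparison p-value. Cmax divided by the actual IU/kg of that visit may be added, though it largely duplicates IVR.

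The cost is one sentence, and two raw parameters lose a p-value. Actual potency, dose and body weight are already collected. The change does not deal with the unequal minimum washout (72 hours at baseline, 48 hours at month 6): among the SAP formulas only IVR subtracts the pre-dose level, so that needs separate treatment.

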7.3 Safety Assessments

7.3.1 Assessments for Safety Endpoints

Any of the following drug safety information shall be collected:

- Adverse events (AEs) and serious adverse events (SAEs) temporally associated with the administration of IMP (for definitions and reporting requirements, see **Sections 7.3.2, 7.3.3, and 7.3.4**)
- Drug overdose, interaction, medication error, and post-study SAEs (see **Section 7.3.7**)

7.3.2 Adverse Events (AEs)

7.3.2.1 Definitions

- **Adverse event (AE):** An AE is any untoward medical occurrence in a study subject/patient receiving an IMP and which does not necessarily have a causal relationship with this treatment. An AE can therefore be any unfavorable and unintended sign (including an abnormal laboratory finding), symptom, or disease temporally associated with the use of an IMP, whether or not related to the IMP.
- **Treatment-emergent adverse event (TEAE):** A TEAE is an AE that started or worsened after the start of IMP infusion.
- **Adverse drug reaction (ADR):** An ADR is any noxious and unintended response to an IMP related to any dose. The phrase ‘response to an IMP’ means that a causal relationship between the IMP and an AE carries at least a reasonable possibility, i.e., the relationship cannot be ruled out.

- **Other significant AEs:** Any marked laboratory abnormalities or any AEs that lead to an intervention, including withdrawal of drug treatment, dose reduction, or significant additional concomitant therapy.
- **Withdrawal due to AE/ADR:** AE/ADR leading to discontinuation of treatment with IMP. Any such events will be followed up by the Investigator until the event is resolved or until the medical condition of the subject/patient is stable. All follow-up information collected will be made available to the Sponsor.

7.3.2.2 Collection of AEs

The condition of the patient will be monitored throughout the study. At each visit, whether scheduled or unscheduled, AEs will be elicited using a standard nonleading question such as “How have you been since the last visit/during the previous study period?” In addition, the Investigator will check the patient diaries for any documented event.

Any AE or ADR which occurs during the study will be noted in detail on the appropriate pages of the CRF. If the patient reports several signs or symptoms representing a single syndrome or diagnosis, the diagnosis should be recorded in the CRF. The Investigator will grade the severity of all AEs or ADRs (mild, moderate, or severe), the seriousness (non-serious or serious), and the causality as defined in **Sections 7.3.2.3, 7.3.3, and 7.3.2.4**. The Sponsor is responsible for assessing the expectedness of each ADR (expected or unexpected) as defined in **Section 7.3.2.5**.

In the event of clinically significant abnormal laboratory findings, the tests will be confirmed and the patient followed up until the laboratory values have returned to normal and/or an adequate explanation for the abnormality has become available.

Diseases, signs and symptoms, and/or laboratory abnormalities already present before the first administration of IMP will not be considered AEs unless an exacerbation in intensity or frequency (worsening) occurs.

The Investigator will provide detailed information about any abnormalities and about the nature of and reasons for any action taken as well as any other observations or comments that may be useful for the interpretation and understanding of an AE or ADR.

7.3.2.3 Severity of AEs

The severity of AEs will be graded as follows:

- **Mild:** an AE, usually transient, which causes discomfort but does not interfere with the patient’s routine activities
- **Moderate:** an AE which is sufficiently discomforting to interfere with the patient’s routine activities
- **Severe:** an AE which is incapacitating and prevents the pursuit of the patient’s routine activities

The grading of an AE is up to the medical judgment of the Investigator and will be decided on a case-by-case basis.

7.3.2.4 Causality of AEs

The relationship of AEs to the administered IMP will be assessed by the Investigator:

- **Probable:** reports including good reasons and sufficient documentation to assume a causal relationship, in the sense of plausible, conceivable, likely, but not necessarily highly probable. A reaction that follows a reasonable temporal sequence from administration of the IMP; or that follows a known or expected response pattern to the suspected medicine; or that is confirmed by stopping or reducing the dosage of the medicine and that could not reasonably be explained by known characteristics of the subject's/patient's clinical state.
- **Possible:** reports containing sufficient information to accept the possibility of a causal relationship, in the sense of not impossible and not unlikely, although the connection is uncertain or doubtful, for example because of missing data or insufficient evidence. A reaction that follows a reasonable temporal sequence from administration of the IMP; that follows a known or expected response pattern to the suspected medicine; but that could readily have been produced by a number of other factors.
- **Unlikely:** reports not following a reasonable temporal sequence from IMP administration. An event which may have been produced by the subject's/patient's clinical state or by environmental factors or other therapies administered.
- **Not related (unrelated):** events for which sufficient information exists to conclude that the etiology is unrelated to the IMP.
- **Unclassified:** reports which for one reason or another are not yet assessable, e.g., because of outstanding information (can only be a temporary assessment).

7.3.2.5 Classification of ADRs by Expectedness

ADRs will be classified by the Sponsor as either expected or unexpected:

- **Expected:** an ADR that is listed in the current edition of the Investigator's Brochure.
- **Unexpected:** an ADR that is not listed in the current edition of the Investigator's Brochure or that differs because of greater severity or greater specificity.

7.3.2.6 Outcome of AEs

The outcome of all reported AEs has to be documented as follows:

1. Recovered, resolved
2. Recovering, resolving
3. Not recovered, not resolved
4. Recovered, resolved with sequelae
5. Fatal
6. Unknown

NOTE: A patient's **death** per se is not an event, but an outcome. The event which resulted in the patient's death must be fully documented and reported, even in case the death occurs within 4 weeks after IMP treatment end and regardless of whether or not it is considered treatment-related.

7.3.2.7 Action(s) Taken

AEs requiring action or therapy must be treated with recognized standards of medical care to protect the health and wellbeing of the patient. Appropriate resuscitation equipment and medicines must be available to ensure the best possible treatment in an emergency situation.

The actions taken by the Investigator must be documented:

(a) General actions taken in the event of an AE

- None
- Medication (other than IMP) or other (e.g., physical) therapy started
- Test performed
- Other (to be specified)

(b) IMP-related actions taken in the event of an AE

- None
- Product withdrawn
- Dose reduced
- Dose increased

The Investigator will follow up on each AE until it has resolved or until the medical condition of the patient has stabilized. Any relevant follow-up information will be reported to the Sponsor.

7.3.3 Serious Adverse Events (SAEs)

A **serious AE (SAE)** is any untoward medical occurrence that at any dose:

- results in death,
- is life-threatening (see below),
- requires hospitalization or prolongation of existing hospitalization,
- results in persistent or significant disability/incapacity,
- is a congenital anomaly/birth defect,
- is another important medical event (see below).

NOTE: The term ‘**life-threatening**’ refers to an event in which the subject/patient was, in the view of the reporting Investigator, at immediate risk of death at the time of the event; it does not refer to an event which may hypothetically have caused death had it been more severe.

In deciding whether an AE/ADR is serious, medical judgment should be exercised. Thus, important AEs/ADRs that are not immediately life-threatening or do not result in death or hospitalization but may jeopardize the subject/patient or may require intervention to prevent one of the other outcomes listed in the definitions above should also be considered serious.

Examples of ‘**important medical events**’ are all suspected transmissions of an infectious agent, which therefore have to be reported as SAE. A suspected virus transmission means that virus antigen has been detected in the patient. A passive transmission of antibodies alone does not constitute a suspected virus transmission. Another such ‘important medical event’ that has to be reported as an SAE is the development of FVIII inhibitors.

